# Data Collection Sheet

## King Vision Video Laryngoscope aBlade System for Use in Children

Subject ID _____ Date: _____	Age: _____	ASA:    I    II    III	Patient sticker
Gender: M F	Weight: _____ kg	Height: _____ cm	PI or Sub-I: _____

### LARYNGEAL VIEW

Cormack Lehane:    1    2    3    4
-------------------------------------

### INTUBATION

King Vision aBlade size:    1    2    2 channeled	Standard laryngoscope blade size:    0    1    2    3
Endotracheal tube size:    2.5    3.0    3.5    4.0    4.5    5.0    5.5    6.0	Brand: _____
Blade tip position:    In vallecula    Under epiglottis	Stylet used:    Yes    No
Ease of ETT passage:    1    2    3    4    5    (1 = very easy; 2 = easy; 3 = neutral; 4 = difficult; 5 = impossible)	
Number of insertion attempts:    1    2    3    (Entry of blade into patient's mouth without the need to remove it once entered)	
Insertion time: _____ (Amount of time from Removal of facemask to the first upstroke of etCO 2 )	
Insertion Technique:  Rotated blade in from side (check all that apply)  External laryngeal manipulation  Rotate ETT counterclockwise (channeled only)  Other: _____	

### SAE/Complications

Intubation: (Check all that apply)	 Laryngospasm  Bronchospasm  Regurgitation/Aspiration	 Gastric Insufflation  Desaturation (SpO 2 ≤ 90%)  Other: _____	 None
PACU: (Check all that apply)	 Sore throat  Horseness  Persistent coughing	 Stridor  Other: _____  None	

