7.0 Statistical Considerations

9.0 Privacy/Confidentiality Issues

10.0 Follow-up and Record Retention

1.0 Background

Airway management is a critical component of anesthesia care. Failure to provide adequate ventilation and oxygenation can lead to death or permanent neurologic disability. Tracheal intubation provides a secure airway that is mandatory for many surgical procedures. Intubation of the trachea requires some type of instrument that permits visualization of the glottic inlet during insertion of the tracheal tube through the larynx and into the trachea. For many decades, the standard laryngoscope has consisted of a handle and a folding blade. The blade may be straight or curved. The purpose of the blade is to displace the tongue and sublingual tissue into the sub-mandibular space to provide the anesthesiologist with direct line-of-sight to the laryngeal inlet. Since the blade exerts pressure and displaces tissue, there is some risk of injury to the oral cavity and pharynx. Difficulty with conventional laryngoscopy can be as high as 13 percent.¹ Advances in imaging technology promoted the design of new laryngoscopes that provide an image of the larynx with indirect line-of-sight. The essence of these devices is a CCD chip or “miniature camera” that is placed at the tip of the laryngoscope. The image is transmitted to a screen for the anesthesiologist to observe. These laryngoscopes have been termed video laryngoscopes. Video laryngoscopes reduce pressure on the soft tissue of the upper airway and provide a high-resolution, wide angle view of the upper airway and larynx. Video laryngoscopes, consequently, decrease the risk of upper airway trauma and improve the ease of tracheal intubation. The first video

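### The intubation complication row does not prompt for esophageal tube placement, and a tube redirected with the blade in place counts as a single attempt

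*SAP*

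**What the plan says.** The SAP is a data collection sheet. Its SAE/Complications section has a row headed "Intubation: (Check all that apply". The named items are laryngospasm, bronchospasm, regurgitation or aspiration, gastric insufflation, and desaturation to an SpO2 of 90% or less. The row also has a free-text *Other* line and a *None* box.

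The INTUBATION section of the sheet defines an insertion attempt as "Entry of blade into patient's mouth without the need to remove it once entered". It defines insertion time as "Amount of time from Removal of facemask to the first upstroke of etCO"2. Ease of tube passage is a five-point score that ends at impossible.

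In the combined protocol, section 1.0 describes the task as "insertion of the tracheal tube through the larynx and into the trachea", and lists a very high first-pass success rate among the device's advantages. Section 2.0 makes device performance in children aged one month to 10 years the purpose of the study, and says that the device may become a standard laryngoscope if performance is satisfactory. Section 5.0 lists the device data to be recorded and refers to the sheet; tube location is not on that list. Section 4.0 plans 100 children in one group, and section 7.0 limits the analysis to descriptive statistics.

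**The concern.** The study's results will be the counts on this sheet. There is no comparator and no modelling, and section 10.0 plans no follow-up period, so an event left off the sheet at intubation cannot be recovered in the analysis.

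Esophageal placement is the event in which the tube does not arrive where section 1.0 says it should. The row asks about five other events by name but leaves this one to memory, and to each investigator's view of whether a misplacement put right at once is a complication at all. *None* can be ticked without the question having been raised.

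The attempt definition adds to this. It counts blade entries, not tube passes. The same child can therefore contribute both an absence of complications and a single attempt, and these are two of the figures on which a reader would judge the device.

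**Working it through.** **1. Can any visible field identify the event?** Take a tube that enters the esophagus, is recognised, and is redirected with the blade still in the mouth.

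| Field on the sheet | What it would show |
|---|---|
| Five named intubation events | No item for tube position. Gastric insufflation or desaturation might be ticked, but neither is specific, and neither need occur if correction is quick |
| *Other* | The event, if the investigator writes it in |
| *None* | Can be ticked |
| Number of attempts | 1, because the blade was not removed |
| Insertion time | A longer time, with no reason recorded |
| Ease of tube passage | A subjective score, with no location |

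Only the unprompted *Other* line can identify the event.

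**2. Inputs for the size.** The only figure from the documents is n = 100 (protocol section 4.0). They give no misplacement rate, no precision target and no figure to reproduce. The true rate p, and the share c of events written under *Other*, are assumptions.

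**3. Effect on the reported proportion.** Assume 3 events in 100 children, for illustration only. The intervals are exact (Clopper-Pearson) 95% intervals. For 0 of 100 the upper limit is 1 − 0.025^(1/100) = 0.036.

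| Events recorded | Reported | Exact 95% interval |
|---|---|---|
| All 3 | 3% | 0.6 to 8.5% |
| 1 of the 3 | 1% | 0.0 to 5.4% |
| None of the 3 | 0% | upper limit 3.6% |

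The 3.6% limit is a valid limit on the misplacement rate only if every event is recorded.

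**4. Effect on a first-attempt figure.** Suppose also that all 100 children had one blade entry and that the 3 tubes were redirected with the blade in place. Counting by blade entry gives 100/100, with lower limit 100 − 3.6 = 96.4%. Not counting the 3 gives 97/100, with interval 100 − 8.5 = 91.5% to 100 − 0.6 = 99.4%.

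**5. Chance that the study records at least one event.** This is 1 − (1 − p·c)^100. For example, p = 0.02 and c = 0.25 give 1 − 0.995^100 = 0.39.

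| Assumed true rate p | c = 1 | c = 0.5 | c = 0.25 |
|---|---|---|---|
| 1% | 63% | 39% | 22% |
| 2% | 87% | 63% | 39% |
| 5% | 99% | 92% | 72% |

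**The case against.** The strongest reply is that the form does have a place for the event. The *Other* line can hold it, and any finite checklist leaves some events to free text. The form is also not blind to consequences: insertion time would lengthen, gastric insufflation and desaturation are prompted, and the attempt count rises if the blade comes out. The harm is conditional, because it needs misplacements to occur and to go unwritten. The documents define no overall complication rate and no criterion for satisfactory performance, so no decision rule is shown to change.

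Most of this stands, and it sets the limits of the point. A reader might infer that the sheet cannot record esophageal placement, or that the complication figures will certainly be too low. Neither follows: *Other* allows recording, and the shortfall depends on what happens and what is volunteered. What the reply does not remove is that no specific, prompted item exists, and that the indirect signals do not say where the tube went.

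A reader might extend the point to placement in a main bronchus. That does not fit section 1.0: such a tube has passed through the larynx and the trachea, so this is a question of tube depth and not the failure described there.

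A reader might also fault the end point of insertion time because it uses the first CO2 upstroke and does not require a sustained trace. Nothing in the documents says that a misplaced tube gives a transient trace. The present end point is clear, and an undefined term such as sustained could make it less reproducible.

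**Conclusion.** The point holds as a gap in prompted data capture. Esophageal placement reaches the data only if volunteered, and a tube redirected with the blade in place counts as one attempt and may be reported as a first-attempt success with no complication. The description of device performance may then be too favourable.

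The size is unknown from the documents. Under the assumed 3 events in 100, the reported proportion falls from 3% to 1% if one event is volunteered, and to 0% if none is. With true rates of 1% to 5%, and only a quarter of events written in, the chance of recording any event is 22% to 72%, against 63% to 99% with complete capture. These figures rest on assumed rates and capture shares, and on children being independent with a common rate.

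This is not a contradiction or a calculation error, and the sample size and type of analysis are unaffected. It is a cheap improvement that bears directly on the study's stated purpose.

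**What to change.** - Add one tick box to the Intubation row: *Esophageal placement (recognised and corrected)*.
- Report it as a count over all children in whom the device was used, with an exact 95% interval.
- State in section 7.0 that a child with this box ticked is not counted as a first-pass success, whatever the number of blade entries.
- Optionally, add a separate box for endobronchial placement, reported on its own as an item about tube depth.
- Leave the end point of insertion time as it is.

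The cost is one tick box and a sentence or two in the analysis section. The downside is that the complication and first-pass figures may look slightly less favourable. The change concerns recording and reporting only and does not alter patient care.

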3.0 Inclusion/Exclusion Criteria

Inclusion:

1. All children between the ages of 1 month to 10 years with a normal preoperative airway examination
2. Scheduled for a surgical procedure that requires tracheal intubation shall be included.

Exclusion:

1. Patients that will be excluded are those with an airway examination or previous anesthesia history that suggests difficulty with mask ventilation.

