4.0 Enrollment/Randomization

100 patients will be enrolled. Data will be collected from the patients that the King Vision Video Laryngoscope is used. As this is not a comparative study, there shall be no randomization.

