5.0 Study Procedures

All procedures shall be routine procedures for the administration of anesthesia appropriate for the age of the child and the type of surgical procedure. This is a data collection only study .

1. The technique of anesthesia induction will be determined for each patient by the anesthesiologist of record.
2. After the induction of anesthesia, and when the patient is at an adequate depth of anesthesia, tracheal intubation will be performed with the King Vision video laryngoscope by one of the investigators.
3. Data recorded will include gender, age, and weight of the patient.
4. Data specific to the device and tracheal intubation include; size and type of blade (standard vs. channeled), blade tip position, Cormack-Lehane score, tracheal tube size, and a subjective scoring of tracheal tube delivery.
5. See the attached data collection sheet.

6.0 Reporting of Adverse Events or Unanticipated Problems Involving Risk to Participants or Others

We do not anticipate adverse events related to this study. This is a data collections only study therefore there are minimal to no risks to the subjects.

There is a minimal risk of loss of confidentiality. PHI will be accessed for recruitment purposes by the clinical care team and/or research care team.

All data shared with the sponsor will be unidentifiable.

Any reports of adverse events can be made to:

[name]. @ Office number: [contact] or [contact]

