7.0 Statistical Considerations

As this is not a comparative study, only descriptive statistics will be applied.

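### PACU throat symptoms are recorded after any eligible operation with no visible item for surgical site, so the overall PACU symptom rate could include symptoms caused by surgery.

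*SAP*

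**What the plan says.** The data collection sheet (document SAP) has two rows under SAE/Complications. One covers events at intubation. The other, headed "PACU: (Check all that apply", offers sore throat, hoarseness, persistent coughing, stridor, other and none. Neither row has a field for cause or relatedness.

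The protocol's Section 3.0 sets eligibility by age, by an airway condition ("with a normal preoperative airway examination") and by the need for intubation: "Scheduled for a surgical procedure that requires tracheal intubation shall be included". The single exclusion is an "airway examination or previous anesthesia history that suggests difficulty with mask ventilation". No surgical site is excluded.

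Section 5.0 says anesthesia will suit the type of surgical procedure, so the protocol expects operations to differ. Its list of data does not include the operation. Item 3 reads "Data recorded will include gender, age, and weight of the patient". Item 4 covers blade, tip position, Cormack-Lehane score, tube size and a subjective score of tube delivery. Item 5 refers to the sheet. The sheet's visible header has identifier, date, age, ASA class, gender, weight, height, investigator and a patient sticker, but no procedure field.

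Section 4.0 states "100 patients will be enrolled" and "As this is not a comparative study, there shall be no randomization". Section 7.0 states that "only descriptive statistics will be applied".

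**The concern.** The PACU symptoms are observed after the whole operation and extubation. Surgery in the mouth, pharynx or airway can plausibly cause the same four symptoms. If such operations are in the sample and are not identified, a descriptive PACU rate adds two sources together, and there is no comparator to show the background level.

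Section 2.0 gives the purpose as evaluating the performance of the device, and says it may become a standard laryngoscope if performance is satisfactory. A reader of the results is likely to take the PACU row as evidence on how gently the device treats the airway. That reading is insecure if the rate can move with the operating list. What is at stake is the interpretation of a secondary safety description. Laryngeal view, ease of tube passage, number of attempts and insertion time are recorded at intubation, before surgery can affect them.

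**Working it through.** **Text check.** The point depends on three facts holding together.

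1. Symptoms that surgery could cause are counted in the PACU: yes (sheet, SAE/Complications).
2. Operations that could cause them are eligible: yes, because nothing excludes them (Section 3.0). The normal-airway criterion limits the child's airway, not the surgical site, though it probably removes some children having airway surgery.
3. The operation is not recorded: true of every visible item on the sheet and of items 3 and 4 in Section 5.0.

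**Illustration of size.** The documents give the sample size, 100, with no derivation, so there is no planned precision or rate to reproduce. They also give no case mix and no symptom rates. The inputs below are therefore assumptions:

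- s, the share of oral, pharyngeal or airway operations: 10% to 50%
- d, the symptom rate from intubation: 5% to 20%
- g, the symptom rate from such surgery: 30% to 90%, taken as independent of d

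Observed rate = (1 − s)·d + s·[1 − (1 − d)(1 − g)] = d + s·g·(1 − d).

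With d = 10% and g = 60%, this is 0.10 + 0.54·s:

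| s | Observed rate | Ratio to d |
|---|---|---|
| 0% | 10.0% | 1.0 |
| 10% | 15.4% | 1.5 |
| 20% | 20.8% | 2.1 |
| 30% | 26.2% | 2.6 |
| 50% | 37.0% | 3.7 |

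Extremes over the assumed ranges:

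- Lowest ratio (d = 20%, s = 10%, g = 30%): 0.20 + 0.10 × 0.30 × 0.80 = 22.4%, which is 1.12 times d.
- Highest ratio (d = 5%, s = 50%, g = 90%): 0.05 + 0.50 × 0.90 × 0.95 = 47.75%, which is 9.55 times d.

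**A simpler mixture as a cross-check.** Assume 80% of children have a symptom after throat surgery and 10% after other surgery. The pooled rate is 0.80·s + 0.10·(1 − s), which gives 17%, 31% and 45% at s = 10%, 30% and 50%. At s = 10%, 10 of the 17 points are baseline and 7 are surgical excess.

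**Against sampling error.** At s = 20%, d = 10% and g = 60%, about 21 of 100 children would be recorded with a symptom (exact 95% interval 13.5% to 30.3%). Intubation alone would give 10 of 100 (4.9% to 17.6%). From the visible items, nobody could tell how much of the 21 came from surgery.

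**What a split would cost in precision.** In the same example the groups have 80 and 20 children. In the 80, 10% is 8 children, with an exact 95% interval of 4.4% to 18.8%, slightly wider than 4.9% to 17.6%. In the 20, the expected rate is 1 − 0.90 × 0.40 = 64%, or about 13 children, with an interval of 40.8% to 84.6%.

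**The case against.** Several things can fairly be said for the plan.

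- **No device complication rate is defined.** This stands. The sheet separates intubation events from PACU events, attributes neither to the device, and gives no instruction to pool them. A reader might infer that the PACU row is the device's complication rate. The documents do not say so, and the point here is only that the row invites that reading.
- **The operation may be recoverable.** The sheet carries a date and a patient sticker, so the chart could probably be traced. This also stands in part: it would be wrong to say that the sources can never be separated. But no plan provides for the look-up, and Section 6.0 says data shared with the sponsor will be unidentifiable.
- **Absence can be claimed only for visible items.** Part of the sheet is not in the available text. Section 5.0 is not exhaustive either: item 3 is worded as inclusive, and the sheet records ASA class, height, attempts and insertion time, which items 3 and 4 omit. This limits confidence, but no visible text contradicts the point.
- **Throat surgery may be rare in this sample.** It is not named anywhere, and the normal-airway criterion probably removes some airway cases. This stands. At the low end of the illustration the inflation is only 1.12 times.

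A stronger reading is tempting: that the PACU rate would reflect the operating list more than the laryngoscope, and so cannot describe the device at all. The documents do not support it. They give no case mix, and even with an assumed 80% symptom rate after throat surgery, a 10% share of such surgery leaves most of the pooled 17% as baseline.

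**Conclusion.** The point holds as a limited one. As far as the visible text shows, the PACU symptom rate could include symptoms caused by surgery, and the listed data would not allow them to be described apart. The size is unknown. Under the assumed ranges the observed rate is between 1.12 and 9.55 times the intubation-related rate. Those figures rest on invented rates, an invented case mix and independence of the two causes, so they show only that the effect could be negligible or large.

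The conclusion assumes that some children in the sample have oral, pharyngeal or airway surgery, and that the part of the sheet not available has no operation field. It does not touch the intubation outcomes. It is worth acting on because the correction is nearly free, not because it undermines the study.

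**What to change.** Add one tick box for surgical site, 'oral, pharyngeal or airway' or 'other', to Section 5.0 item 3 and to the header of the data sheet. State in Section 7.0 that PACU symptoms will be reported for all children and separately by surgical site.

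Add a note to that table that symptoms in the 'other' group still reflect the tube and extubation as well as the laryngoscope, since a single-arm study cannot isolate the blade. Keep the all-children figure, because describing symptoms from the 'other' group alone would drop treated children from the safety description.

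The cost is one extra field and one split table, with smaller denominators and therefore wider intervals in the split.

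### The data sheet records throat and airway symptoms only in PACU, with no preoperative entry, so symptoms present before surgery can enter the complication rate and the form cannot separate them.

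*SAP*

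**What the plan says.** The Data Collection Sheet (filed as the SAP) collects postoperative symptoms in a single row, "PACU: (Check all that apply)". The boxes are sore throat, hoarseness, persistent coughing, stridor, other and none. The row sits under the heading "SAE/Complications". It has no field for whether a symptom is new, worse than before, or related to the intubation.

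The sheet's header holds age, ASA class, gender, weight and height. Section 5.0 of the protocol gives a shorter list of patient data, "Data recorded will include gender, age, and weight of the patient", and then turns to the device and the intubation. Neither place contains a symptom history.

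Section 3.0 admits "All children between the ages of 1 month to 10 years with a normal preoperative airway examination" who are scheduled for surgery that needs tracheal intubation. Its only exclusion is an "airway examination or previous anesthesia history that suggests difficulty with mask ventilation".

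On size and design, Section 4.0 states "100 patients will be enrolled" and "As this is not a comparative study, there shall be no randomization". Section 7.0 limits the analysis to descriptive statistics and has no rule for counting or attributing complications.

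**The concern.** A tick in the PACU row shows that the symptom was present after surgery. It does not show whether the symptom was already there before. A child who arrives with a cough and still has it in PACU can be ticked in the same way as a child who begins coughing after intubation. No instruction on the form says to tick or to omit a symptom known to be old, so recorders may also differ.

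A concurrent control group would show the background level of such symptoms. Here there is none, so the reported proportion is read at face value. This matters because Section 2.0 says that satisfactory performance could lead to the device becoming a standard laryngoscope. Section 1.0 argues that video laryngoscopes cause less upper airway trauma. The PACU row is the sheet's only postoperative record that bears on that argument.

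**Working it through.** **Step 1. Does any part of the plan capture or screen out the symptoms beforehand?**

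| Place | What it gives | Separates old from new? |
|---|---|---|
| Sheet, header | Age, ASA class, gender, weight, height | No; ASA class names no symptom |
| Sheet, PACU row | Four symptoms, present or absent, after surgery | No |
| Section 3.0, inclusion | Normal preoperative airway examination | In part; it may remove some children, most plausibly those with stridor, but is not defined as covering cough, sore throat or hoarseness |
| Section 3.0, exclusion | Expected difficulty with mask ventilation | No |
| Section 5.0 | Gender, age, weight, device and intubation data | No |
| Section 7.0 | Descriptive statistics | No |

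The public text has parts removed, so the absence of a baseline entry is judged on what is visible.

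**Step 2. Size.** The plan has no figure to reproduce: it gives no symptom rate, and the 100 is stated without a derivation. What follows is an illustration on assumed inputs.

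- b = share of children with the symptom beforehand in whom it persists into PACU and is ticked. Assumed 0%, 2%, 5%, 10%.
- t = true rate of new symptoms. Assumed 5%, 10%, 20%.
- b and t are taken as independent.

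Recorded rate = 1 − (1 − b)(1 − t). Excess over the true rate = b(1 − t).

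Example: b = 5%, t = 10% gives 1 − 0.95 × 0.90 = 14.5%, an excess of 4.5 per 100.

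| b | Recorded, t = 5% | Recorded, t = 10% | Recorded, t = 20% | Excess per 100 (t = 20% to t = 5%) |
|---|---|---|---|---|
| 0% | 5.0% | 10.0% | 20.0% | 0 |
| 2% | 6.9% | 11.8% | 21.6% | 1.6 to 1.9 |
| 5% | 9.75% | 14.5% | 24.0% | 4.0 to 4.75 |
| 10% | 14.5% | 19.0% | 28.0% | 8.0 to 9.5 |

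**Step 3. Would any child be affected at all?** The chance that at least one of 100 children is affected is 1 − (1 − b)^100. That is 86.7% at b = 2% and 99.4% at b = 5%. At b = 0% it is zero.

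**Step 4. Effect of a baseline entry.** Among children without the symptom beforehand, the PACU proportion estimates t directly under the same independence assumption. The expected denominator is 100(1 − b): 98, 95 or 90 children at b = 2%, 5% or 10%.

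**The case against.** The strongest reply is that a complication, in its ordinary sense, arises from care. A recorder who knows that a child came in coughing may leave the box empty. The airway examination required for entry also removes some children with symptoms. Both points stand as partial protection, and they are why the range for b starts at 0%. Neither is written down as a rule for these four symptoms, so they reduce the problem without closing it.

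It is also fair to say that the stated aim is to describe performance. No complication rate is named as an endpoint, and no threshold depends on the PACU row. That limits the importance of the point but does not make the row interpretable.

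A reader might infer four stronger things, which the documents do not support:

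- *That the plan attributes these symptoms to the device.* The heading is general, and nothing in either document assigns PACU symptoms to the laryngoscope.
- *That the rate is inflated several-fold.* A large ratio needs a low true rate combined with a high prevalence. At t = 20%, b = 2%, 5% and 10% give 21.6/20 = 1.08, 24/20 = 1.2 and 28/20 = 1.4 times; at b = 0% there is no inflation.
- *That the baseline is lost for good.* The sheet carries a patient sticker, so each form can be linked to a patient whose chart may hold a symptom history. The documents do not show what the chart contains. What they support is that the study form alone cannot separate old from new.
- *That respiratory infection distorts the intubation events as well.* The documents say nothing about such a link, so the point here is confined to the four PACU symptoms.

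**Conclusion.** The point holds in a limited form. The form has no preoperative entry and no new-onset field for the four symptoms, and eligibility does not exclude children who already have a cough, sore throat or hoarseness. The PACU complication rate can therefore mix old and new symptoms. If it does, the error is upward, and with one arm there is no background rate to set against it.

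The size cannot be derived from the documents. On the assumed inputs it runs from 0 to 9.5 per 100 children. This rests on independence of old and new symptoms, on the old symptom persisting into PACU, and on the recorder ticking it. It is an inexpensive improvement to a safety description, and the study's main performance data do not depend on it.

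**What to change.** 1. **Data Collection Sheet.** Add one line, headed Before induction, with the same four symptom boxes and a box for none. Complete it at the preoperative airway examination that Section 3.0 already requires.
2. **Section 7.0.** Add a sentence: each PACU symptom is reported as new-onset (absent before induction, present in PACU) among children without that symptom at baseline, with numerator and denominator, alongside the count in all children. The second count keeps in view the children who had the symptom at both times.

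The cost is one extra line on the form and a slightly smaller denominator for each symptom. Eligibility, sample size and clinical care do not change.
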